## **PRELIMINARY DATA**

None

## **PARTICIPANTS**

### **Recruitment**

Participants will be patients recruited from the Vancouver General Hospital (VGH) Colposcopy Clinic who present for their initial colposcopy visit. Initial visits are already marked on the current clinic booking system utilized by the clinic healthcare providers. A clinical and research nurse who has previously been involved in recruitment of patients for other studies in the clinic will approach patients who meet inclusion criteria before or after their appointment as time permits and as patients prefer. Patients will be provided with a copy of the consent form that contains information about the study and the invitation to participate and will be given an opportunity to ask questions. Patients may then decide to participate in the study on the same day as their appointment and be consented by the research nurse in the clinic. The nurse will explicitly inform them that should they later choose to withdraw their consent, this may be done at any time with no impact on the care they receive. The decision of whether to participate will not impact any colposcopy visit that follows. All patient information will be stored on a password protected computer in an encrypted, password protected file. Following consent, patients will be randomized to the patient liaison intervention or control group. Thus, control participants will be recruited in the same manner as the intervention group participants.

### **Inclusion Criteria**

1. Must be 19 years of age or older
2. Must be patients presenting for an initial visit at the VGH Colposcopy Clinic

### **Exclusion Criteria**

1. Inability to speak conversational English- required to complete the questionnaire as well as provide informed consent to participate
2. Inability or refusal to provide consent
3. Pregnant – pregnant women do not usually have biopsies and their subsequent care may be much different than non-pregnant patients
4. Do not have a family physician or referring physician who will provide continuity of care following colposcopy – these patients do not have the option of getting results from a family or referring physician, so they would bias results.

## **Retention**

Recruitment is anticipated to commence in May or June 2017. With an anticipated 20-30 new patients per week in the VGH Colposcopy Clinic and capacity for nurses to approach 50% of these (10-15 patients per week), recruitment of 400 patients (with a 50% participation rate of 200 patients total) will be completed over approximately 9 months and be targeted for completion by the end of 2017. Each patient will be followed for approximately 6 months following their initial colposcopy visit via chart review at that interval, as it is anticipated that any recommended treatments or follow-up visits will take place by 6 months per the clinic standard. Thus, we anticipate completion of the trial by July 2018 for a total of 18 months.

## **Consent**

Consent will be obtained by the colposcopy research nurse at the VGH Colposcopy Clinic who will make initial contact with each patient in the waiting room prior to, or following, the colposcopy visit. After the patient has been presented with a consent form that includes information about the study and an invitation to participate, they will be given the opportunity to ask questions regarding participation in the study. Should they be interested in participating, the nurse will then review the consent form and the patient will be given the opportunity to sign the consent at that time. They will be informed that should they decline to participate or wish to withdraw their consent, they may contact the clinic to do so at any time and there will be no impact on the care they receive.

## **Use of Records**

Patient charts from Vancouver General Hospital (VGH) records will be extracted by [name] under the supervision of the Principal Investigator ([name]) who is a physician in the colposcopy group, and has access to clinical charts on routine basis. In the current standard practice at the VGH Colposcopy Clinic, patient electronic and paper charts are shared and utilized within the group of colposcopists in the direct provision of care and routine charting, and patients frequently will see a different physician for a follow-up appointment than for an initial visit. The key information to be drawn from the patient charts includes information regarding attended or missed follow-up appointments and adherence to follow-up and treatment recommendations-- this is already routinely collected and tracked by the clinic in order to optimize clinic efficiency and patient care. Additional information to be extracted from the patient chart within 6-12 months of the initial colposcopy visit includes the final pathologic result and pathologic diagnoses associated with any treatments, which will be used to compare patient self-reported colposcopy results to the actual results as well as assess the impact of patient adherence on clinical outcomes. Permission to access and utilize these clinical data will be obtained in the initial consent to participate in the study.

## **Criteria for Early Withdrawal of Participants**

Should any participant request to withdraw from the study prior to being contacted with their results by either the patient liaison or their family/referring physician, this will be noted on the colposcopy clinic chart and they will default to the clinic standard of care (upon generation of the colposcopy report, a note will be sent to the family/referring physician informing them that they must follow-up with the patient regarding their colposcopy results).

## **SAMPLE SIZE CALCULATION**

To achieve 90% power for a difference of 5.3 (half of a standard deviation is considered clinically significant) in mean anxiety scores (state subscale of the STAI) between the control and intervention groups with an assumed pooled standard deviation of 10.6 and alpha of 0.05, the required sample size is 85 per group. Accounting for about 15% loss to follow-up, we aim to recruit 100 per group with 200 participants in total. With an estimate of 50% participation, the research nurse will need to attempt to recruit approximately 400 patients to reach this target.

## **ANALYSIS**

The mean composite scores will be compared between the intervention and control groups with a significance level  $p<0.05$  specifically looking at:

- 1) Mean patient anxiety (quantified by the STAI state subscale and HAI scale) related to receipt of colposcopy results: The State Trait Anxiety Inventory is an established and widely-used anxiety measure with high internal consistency (Cronbach's  $\alpha = 0.83-0.95$  dependent on the population studied). It contains 20 self-reported items that measure situational or state anxiety, and patients rate their agreement with these statements on a four point Likert scale which are then aggregated for a composite score. Mean composite trait and state anxiety scores will be compared between the two groups using the two-tailed t-test.
- 2) Patient satisfaction with the timing and method of communication of their colposcopy results and satisfaction with the information they received concerning their diagnosis, procedures, or recommended management: these will be quantified by the validated PSQ-18 and VSQ-9 scales which have been previously used in patient satisfaction studies at the VGH Colposcopy Clinic. Mean scores on the subscales will be compared between the two groups using the two-tailed t-test.
- 3) The accuracy of participant understanding of their colposcopy diagnosis following the intervention: for all patients, self-reported colposcopy diagnosis will be compared to the diagnosis in the clinic chart and graded as correct or incorrect. A chi-square analysis will be performed to assess whether there is a significant difference between the two groups.
- 4) Timeliness and rates of communication of patient results: The mean interval in days between generation of colposcopy reports and the communication of the result to the patient as well as the mean percentage of successfully contacted participants will be compared between the two groups using t-tests and z-tests.
- 5) Participant adherence to follow-up: patient electronic charts will be reviewed in 6-12 months following the colposcopy. The proportion of patients who complete the recommended follow-up will be compared between groups using z-test.

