### **STUDY DESIGN AND METHODOLOGY**

This is phase two of a two-part study. The first phase employs qualitative methodology with focus groups. Themes from these focus groups will inform development of the nurse-led patient liaison intervention to be employed in the second phase. The first phase has been reviewed in a separate Ethics application (REB#H16-01422).

This is a randomized controlled trial to compare patients who participate in the patient liaison intervention (intervention group) to those who continue with the current system of results reporting via the family/referring physician (control group). Following recruitment and consent, patients will be randomized to the intervention or control group. The control group will receive the standard of care for colposcopy results reporting via their referring physician. Following their

colposcopy visit, control patients are given a slip of paper reminding them to call their family/referring physician for their colposcopy results in three weeks if they have not yet been contacted. Upon receipt of the final pathology, colposcopy reports are prepared by the colposcopists and forwarded to family/referring physicians typically within 2-3 weeks of the visit. Patients then receive the results of their colposcopy report from their family/referring physician by whatever method of communication preferred by that provider.

The participants randomized to the intervention group will be exposed to the patient liaison in receiving their colposcopy report results and recommendations. Rather than receive results from their referring/family physician, an experienced colposcopy nurse will contact participants once the colposcopists complete the final colposcopy report. The colposcopy report will inform the referring provider that these patients will be informed of the results. The colposcopy nurse will provide an explanation of the colposcopy results and subsequent follow-up or treatment recommendations, be available to answer patient questions (within her scope), offer educational or support resources to patients. She will forward any patient questions beyond her scope to the patient's colposcopist who may then provide answers to the patient liaison or to the patient directly depending on the complexity and nature of the question.

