The research coordinator ([name]) will subsequently contact all participants (control and intervention groups) to complete a questionnaire following the communication of their colposcopy report. All participants following consent will be asked to provide their preferred contact method (email, telephone) and whether they prefer to access the questionnaire via an Internet link sent to their email or to complete it verbally via telephone with the research coordinator. Control participants will be contacted within 3-4 weeks of their initial colposcopy visit to permit time for communication of their results from their family/referring physician. Intervention group participants will be contacted once the patient liaison nurse has informed the research coordinator that the results have been communicated to the participant. Reminders to complete the questionnaire will be sent at weekly intervals—twice via email, and a third time via telephone. Patients who fail to complete the questionnaire after three reminders will be considered lost to follow-up.

- 1) The questionnaire will contain the following information and validated scales:
  - (a) Demographics\*
  - (b) Date of colposcopy appointment and date that results were communicated (to measure the time interval in days in which results were received by participants)
  - (c) Method of colposcopy results communication – family/referring MD versus patient liaison (to determine intention to treat versus per protocol)
  - (d) State-Trait Anxiety Inventory (STAI)
  - (e) Health Anxiety Inventory (HAI)
  - (f) Short-Form Patient Satisfaction Questionnaire (PSQ- 18)
  - (g) Patient Satisfaction Survey (VSQ-9)
  - (h) Self-reported colposcopy result and recommendation (to be compared to actual result on file)

\*Demographic information collected will include: Age, highest level of education, current employment, and ethnicity. This information is necessary to understand sample diversity, and generalizability of results.

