Secondary aims in the randomized trial will be to assess the effectiveness and clinical impact of the patient liaison intervention by comparing: 1) the interval between generation of colposcopy reports and communication of these results to patients; 2) percentage of patients successfully contacted and number of contact attempts both by the patient liaison nurse and the research coordinator administering the questionnaire; 3) the accuracy of patient's understanding of their colposcopy result, measured by the comparison of self-reported and actual result; and 4) rates of patient compliance with recommended follow-up appointments for treatment or repeat colposcopy. Patient electronic charts will be reviewed in 6-12 months following the initial colposcopy visit to collect data regarding histologic diagnoses, adherence to subsequent follow-up or treatment appointments and number of missed/cancelled appointments.

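### The between-arm test of percentage successfully contacted compares contacts that arise differently in the two arms, so it can be distorted in either direction

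*Protocol*

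**What the plan says.** Item 4 of the protocol's ANALYSIS section is headed "Timeliness and rates of communication of patient results". It plans a comparison of the interval from report to communication and adds that "the mean percentage of successfully contacted participants will be compared between the two groups using t-tests and z-tests". It states no contactor, denominator or time window.

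The secondary aims under STUDY DESIGN AND METHODOLOGY say which contacts are meant: "percentage of patients successfully contacted and number of contact attempts both by the patient liaison nurse and the research coordinator administering the questionnaire". The family or referring physician is not listed.

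The same section sets out how contact arises in each arm:

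- **Results, controls:** "The control group will receive the standard of care for colposcopy results reporting via their referring physician". The physician passes them on "by whatever method of communication preferred by that provider", and no log of attempts is described.
- **Coordinator, controls:** "Control participants will be contacted within 3-4 weeks of their initial colposcopy visit".
- **Coordinator, intervention:** "Intervention group participants will be contacted once the patient liaison nurse has informed the research coordinator that the results have been communicated".

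The date and method of communication are questionnaire items. EARLY STOPPAGE foresees that the nurse may miss some participants and sets a threshold of 15% or more at the interim look. The SAP gives generic tests for secondary outcomes (t-test or Fisher's exact) and does not name or define a contact rate.

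**The concern.** A between-arm test needs a quantity that arises in the same way in both arms. Liaison contact has no control value. Coordinator contact has a value in both arms, but in the intervention arm it must first pass through the nurse: someone she never reaches never triggers the coordinator, and controls face no such filter. A difference could therefore appear when participants are equally reachable in both arms, or a real one could be hidden. Since the intervention is meant to improve how results are communicated, a spurious difference here could be read as evidence about whether it works, for or against.

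**Working it through.** **The plan's own figures.** The documents give no figure for the contact-rate comparison. The only sample size concerns the STAI state score: n per group = 2 × (1.960 + 1.282)² × (10.6/5.3)² = 2 × 10.51 × 4 = 84.1, so 85, and 85/0.85 = 100. Both reproduce. They are used below only as 100 randomised and 85 responders per arm.

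**Test.** Pooled two-proportion z = (p₁ − p₂) / √[p(1 − p)(1/n₁ + 1/n₂)], two-sided, where p is the pooled proportion.

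**Assumed inputs.** Contact rates are not in the documents. I let the coordinator be able to reach a share c = 85% to 95% in both arms, so there is no true difference, and let the nurse reach r = 85% to 100%. The only related figure in the protocol is the 15% stopping threshold, which corresponds to r = 85%.

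**Step 1: single examples.** The nurse reaches the same share of the intervention arm as the coordinator reaches of controls. The coordinator then reaches about 95% of those the nurse reached.

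| Share reachable | Denominator: nurse-reached | Denominator: all randomised |
|---|---|---|
| 85% | 81/85 v 85/100, z = 2.30, p = 0.02 | 81/100 v 85/100, z = −0.75, p = 0.45 |
| 90% | 86/90 v 90/100, z = 1.46, p = 0.14 | 86/100 v 90/100, z = −0.87, p = 0.38 |
| 95% | 90/95 v 95/100, z = −0.08, p = 0.93 | 90/100 v 95/100, z = −1.34, p = 0.18 |

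For the first cell, p = 166/185 = 0.897, the standard error is 0.0448 and the difference is 0.103. Fisher's exact test, which the SAP would use, gives p = 0.028 there. If the coordinator reached all 85, the nurse-reached comparison would be 85/85 v 85/100 (p = 0.0002) and the all-randomised one 85/100 v 85/100 (p = 1.0).

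**Step 2: how often the z-test rejects with no true difference in reachability.** Exact binomial enumeration, c = 90%, 100 randomised per arm:

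| Nurse reaches r | All randomised, nurse and coordinator contact independent: intervention rate r × c, rejection | Nurse-reached only, same people hard to reach for both: intervention rate, rejection |
|---|---|---|
| 100% | 90.0%, 5% | 90.0%, 5% |
| 95% | 85.5%, 16% | 94.7%, 23% |
| 90% | 81.0%, 45% | 100%, 98% |
| 85% | 76.5%, 74% | 100%, 98% |

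The control rate is 90% throughout. The middle column errs against the intervention and the right-hand column in its favour. Over c = 85% to 95% and r = 85% to 95%, rejection in the middle column runs from 13% to 90%.

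The distortion vanishes in three cases: the nurse reaches everyone; the denominator is nurse-reached and the two contacts are independent; or the denominator is all randomised and the nurse reaches everyone the coordinator could.

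**Step 3: the any-route reading.** Suppose receipt is taken from 85 questionnaire responders per arm. Intervention participants are invited only after being informed, so I take their rate as 100%. If 85%, 90% or 95% of controls are informed, the z-test rejects 99.9%, 97.5% or 62% of the time, even if true receipt among all randomised participants is equal.

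**The case against.** The strongest reply is that item 4 can be read as receipt of the result by any route. Its heading speaks of communication of results, and the section on early withdrawal describes participants being contacted with their results by either the liaison or the physician. On that reading both arms have a value. This stands as a reading, and it rules out saying that the outcome is simply undefined. It does not make the data comparable, as step 3 shows.

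A reader might also infer that the test is biased in favour of the intervention by construction. The documents do not support that. No section restricts the denominator to nurse-reached participants, and the protocol says that the coordinator will contact all participants in both groups. With everyone randomised in the denominator, the illustrated benefit disappears or reverses. The most striking examples also need r = 85%, which is at the stopping threshold, and strong overlap between the people each caller can reach.

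Finally, the contact percentage is not among the outcomes listed under HYPOTHESIS AND OUTCOMES, and it drives neither the sample size nor the primary test. That is correct and limits the weight of the point. It remains a stated secondary aim with a committed between-arm test.

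**Conclusion.** The point holds as a defect in a secondary process measure. It is more than missing detail, because a stated rule (calendar trigger in one arm, nurse success in the other) makes the coordinator's contacts non-comparable whichever denominator is chosen, except in the special cases listed in the working. The direction is not fixed: the comparison can favour the intervention with a nurse-reached denominator, and it is neutral or unfavourable to it with all randomised participants. The sizes shown rest on assumed contact rates and on how far nurse and coordinator contact overlap, neither of which the documents give. The definition of this outcome does not directly affect the primary t-test, although the same rule also determines which intervention participants are invited to the questionnaire.

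**What to change.** 1. **Replace the test.** Use one secondary process endpoint: result received from any source by a fixed day after the visit, among all randomised participants. Compare the arms with a two-proportion or Fisher's exact test and a confidence interval.
2. **Match ascertainment.** Use the same data source in both arms and the same calendar-based coordinator contact, including intervention participants whom the nurse could not reach. An all-randomised denominator alone does not remove the filter.
3. **Handle unknown receipt openly.** Show results under alternative assumptions. Counting every unknown as not received is not neutral. With true receipt of 95% in both arms, a nurse log in one arm gives 95/100, while questionnaire data with 15% loss in the other gives 0.95 × 0.85 × 100 ≈ 81/100: z = 3.05, p = 0.002.
4. **Describe, do not test, liaison contact.** Report the liaison's contact rate and number of attempts in the intervention arm only.
5. **If data were already collected under the differing triggers**, as the SAP's past tense suggests, report coordinator contact rates by arm without a p-value, with all randomised participants as the denominator, and state the trigger rule beside them.

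The cost is protocol and SAP wording plus a little more analysis, since date and method of communication are already questionnaire items. If recruitment were still open, the coordinator would also have to contact intervention participants whom the nurse missed. The downside is a less precise estimate of receipt where receipt is unknown.

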## **BENEFITS**

Those who participate in the patient liaison intervention may benefit from more timely receipt of their colposcopy results and recommendations as well as an improved understanding of their pathology, the rationale for the recommendations, and support in the logistics of arranging their follow-up or treatment visits. The direct contact with the experienced colposcopy nurse who can offer support and counseling may also improve the overall patient satisfaction with the experience of receiving their results as well as decrease the anxiety or other negative emotions associated with the colposcopy process. They may also have the opportunity to access additional educational or support resources provided by the colposcopy nurse. Improved adherence to colposcopy follow-up and treatment may improve clinical outcomes for patients who participate in the intervention.

## **RISKS**

By participating in the Patient Liaison intervention, the intervention group will no longer primarily receive their colposcopy results from their family/referring physician and may thus experience decreased continuity of care with their referring physician. However, the referring physician will still receive a copy of the colposcopy results and recommendations; while they will be informed that the colposcopy nurse has already contacted the patient, patients will still be able to contact their referring physician or schedule additional follow-up visits at their discretion. During the intervention in which the patient liaison contacts the patient with her results, it is possible that the patient may have questions or concerns which are beyond the scope of the colposcopy nurse. To mitigate this, the colposcopy nurse will be supported by the colposcopists who are most responsible provider for each patient who can provide additional information or resources as needed. The nurse may then attempt to re-contact the patient at a later time, or request permission for the patient to be contacted directly by their colposcopist. In addition, there may be questions that are outside the scope of colposcopy care and patients will be asked to contact their primary care provider in these cases. Patients may encounter questions that they do not feel comfortable answering when completing the questionnaire. Should this occur, patients will be instructed that they may leave these unanswered, or at any time withdraw from the study. The final page of the questionnaire will include investigator contact information for any participant questions or concerns and will also list mental health resources for participants who are seeking further support.

